### **Location 2 -Physical and Cognitive Testing Performed at CCHMC Human Performance Laboratory**

#### ***Station I: Anthropometric Measurements.***

Anthropometric measures will be recorded at Station IV. Height, weight, and body composition (bioelectrical impedance) will be recorded and body mass index (BMI) calculated.

**Height:** A measure of height will be recorded with a digital stadiometer (accurate to 0.25 cm).

**Weight:** A measure to the nearest 0.5 kg will be taken on a calibrated physician scale with the participants' shoes off.

**Neck Measurement:** We will measure the circumference of participant's neck with a measuring tape.

### ***Station II – Oculomotor Assessment***

All participants will sit in front of a desktop monitor. During this process, the participant will look at several points in order to calibrate the desk-top eye tracker (Tobii X2 60). All participants will participate in three oculomotor performance tests: (1) a reflexive saccade test, (2) a self-paced saccade test, and (3) a smooth-pursuit tracking test. All tests will be presented on a PC monitor approximately 1.5 m away from participant, and stimuli will be automated using customized *MATLAB* (Mathworks, Natick, MA) routines.

*Reflexive Saccades.* Reflexive saccades will be tested as participants track discrete target motion that will jump randomly by 14, 16, 18, 20, 22, or 24° on the screen in a horizontal and vertical direction, at intervals varying pseudo randomly between 1.0 and 2.0 s. The current fixation target will be extinguished at the same time as the next peripheral target appears. The test sequence will take 30 s/trial (2 trials) and all participants will be instructed to follow the targets as quickly and accurately as possible. Dependent measures for reflexive saccades will include: (1) saccade latency (ms), (2) saccade velocity (°/s), (3) mean absolute position error of the final eye position, (4) gain of the primary saccade, and (4) gain of the final eye position.

*Self-paced saccades.* Self-paced saccades will be assessed as the participant glances back and forth as quickly and accurately as possible between two constantly visual targets at  $\pm 15^\circ$  horizontally from one another. This test will take 30 s per trial and the participant will perform 4 trials. The dependent measures will be: (1) the number of refixations within 30 s, and (2) the mean intersaccadic interval (ms).

*Self-paced saccades combined with smooth pursuit tracking.* A series of self-paced saccade tasks will be presented in which either, (1) a stationary and moving target (horizontal or vertical) is presented, (2) two horizontally moving target are presented, or (3) two vertically moving targets are presented. The participant will be instructed to glance back and forth between the targets as quickly and accurately as possible. Each test will take 30 s per trial and the participant will perform a total of 22 trials over ~ 11 min. The dependent measures will be: (1) the number of refixations within 30 s, and (2) the mean intersaccadic interval (ms), (3) average eye peak velocity (°/s) after removal of all saccades from the tracking performance, and (4) the tracking lag (ms). Total oculomotor testing time will take approximately 10 minutes, and all eye data will be recorded using Tobii Studio software and will be sampled at 60 Hz.

**ADHD rating scale:** The ADHD rating scale queries parents how often their child exhibits each of the DSM-V ADHD symptoms on a 4-point Likert scale.

Menstruation Questionnaire – In order to determine the status of menstrual cycle, each participant will complete a questionnaire monthly, while participating in the study. Answers from this questionnaire will allow study staff to determine the approximate status of their cycle. This questionnaire will be administered using the electronic data capture REDCap. REDCap is a secure, web-based application for building and managing online surveys and databases. It is a resource of the Center for Clinical and Translational Science and Training (CCTST) provided to researchers. Subjects will be emailed the link to complete the questionnaire each month during participation in the study. All data will be de-identified via a study ID, assigned to each participant when enrolled in the study. Participants will also complete a Pre-Season Menstruation Questionnaire at the first study visit.

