***Statistical considerations.*** The data analysis will begin with a review of descriptive statistics for all major variables and all major subgroupings of variables in the data set. For the inferential methods, we will use a number of different generalized linear modeling techniques, including linear regression models. All analyses will be conducted using SAS® version 9.3 (SAS Inst, Cary, NC), or Mplus (Muthén, 2007). Initial analyses will be undertaken to inspect data for errors, inconsistencies, and incomplete information. This will include examining the data with simple frequency tables and dot plots for univariate data and scatter plots and multi-way dot plots for bivariate and multivariate data. Data anomalies that cannot be resolved by the Biostatistical/data management team will be sent as queries via

email to the project investigator for clarification and/or correction. During the verification process, outlying values will be corrected if necessary. Incomplete information will be corrected and the project investigator will receive updates. To summarize bivariate relationships among predictors and between predictors and outcomes, Chi-square of Fisher's exact test or Spearman's rank correlation coefficient, will be used, as appropriate. For reporting inferential statistics, such as differences in rates or means, 95 percent confidence intervals will be used extensively to quantify degree of clinical efficacy. Unless otherwise stated, statistical tests are considered two-sided and a .05 significance level is used. All models will be adjusted for potential independent predictor variables but will be limited to the number of predictors we can fit in a regression model while maintaining a valid and reliable model. Candidate predictors include amount of playing time, amount of practice time, previous mTBI, weight, age and height. Collinearity will be examined. Linearity assumptions will be checked and transformations examined. In those cases, a log transformation, polynomial terms, or restricted cubic splines will likely be used to relax the assumption of linearity in the regression models. We will remove the nonlinear terms or transformation only if the nonlinear test is non-significant with a  $p \geq .10$ . Additionally, overly-influential observations and distributional assumptions will be checked. Models will be interpreted graphically, predicted values will be examined, and appropriate significance tests will be utilized.

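### The stated 1.5 m viewing distance, a desktop monitor of unstated size and vertical target jumps of 14–24° do not fit together, so part of the oculomotor test cannot be run as written

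*Combined protocol and SAP*

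**What the plan says.** Section (8), Station II – Oculomotor Assessment, describes the display twice: "All participants will sit in front of a desktop monitor", and "All tests will be presented on a PC monitor approximately 1.5 m away from participant". In the reflexive test the target will "jump randomly by 14, 16, 18, 20, 22, or 24° on the screen in a horizontal and vertical direction". The self-paced test has the participant look to and fro between a pair of fixed targets. Their separation is given as ±15°, followed by the words "horizontally from one another. This test will take 30 s per trial". A third test adds targets that move horizontally or vertically, with no amplitude given.

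The reflexive outcomes include latency, velocity in °/s, "mean absolute position error of the final eye position", "gain of the primary saccade" and the gain of the final eye position. The self-paced outcomes are a count of refixations and an interval in milliseconds. Section (9), Oculomotor Measures, plans a group-by-session mixed-model ANOVA for each dependent variable.

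The protocol does not give the monitor's size or shape, the rule for converting screen distance to degrees, or a formula for gain.

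**The concern.** An angle and a viewing distance together fix the length of screen that a jump needs. At 1.5 m, jumps of 14° and more take up a lot of screen, and the short side of a desktop monitor has to hold the vertical ones. If they do not fit, the test cannot be delivered as specified and someone must change it: shorten the jumps, leave out vertical trials, or move the chair forward. The protocol does not say which, and does not ask for the distance to be measured.

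At stake are outcomes expressed in degrees. The abstract counts functional testing, alongside imaging, as evidence of effectiveness. A change of distance between the preseason and postseason visits that nobody recorded would enter the comparison over time.

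**Working it through.** **Inputs from the protocol (Station II):** distance D = 1.5 m; jumps of 14, 16, 18, 20, 22 and 24°, horizontal and vertical; self-paced targets at ±15°; a desktop or PC monitor.

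**Assumption:** the monitor size is not stated. I took 19 to 32 inches (diagonal) as the desktop range, mainly 16:9, with 16:10 and 5:4 also tried. The plan states no on-screen span, so there is no figure of its own to reproduce.

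**Step 1. Screen needed.** The most favourable layout centres the jump on the line of sight: span = 2 × D × tan(angle/2).

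- 14°: 2 × 1.5 × tan 7° = 36.8 cm
- 16°: 42.2 cm; 18°: 47.5 cm; 20°: 52.9 cm; 22°: 58.3 cm
- 24°: 2 × 1.5 × tan 12° = 63.8 cm
- ±15° read as 30° apart: 80.4 cm; read as 15° apart: 39.5 cm

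If 24° jumps start at screen centre and go either way, 2 × 1.5 × tan 24° = 133.6 cm is needed.

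**Step 2. Screen available.** A 16:9 screen has height 0.490 × diagonal and width 0.872 × diagonal. Largest centred angle = 2 × arctan(dimension / (2 × 1.5 m)).

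| 16:9 diagonal | Width × height (cm) | Horizontal | Vertical | Vertical jumps that fit |
|---|---|---|---|---|
| 19 in | 42.1 × 23.7 | 16.0° | 9.0° | none |
| 22 in | 48.7 × 27.4 | 18.4° | 10.4° | none |
| 24 in | 53.1 × 29.9 | 20.1° | 11.4° | none |
| 27 in | 59.8 × 33.6 | 22.5° | 12.8° | none |
| 30 in | 66.4 × 37.4 | 25.0° | 14.2° | 14° only |
| 32 in | 70.8 × 39.8 | 26.6° | 15.1° | 14° only |

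**Step 3. Break-even sizes (16:9, 1.5 m).** Vertical 14° needs 29.6 in and vertical 24° needs 51.2 in. Horizontal 24° needs 28.8 in. Self-paced targets 30° apart need 36.3 in.

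**Step 4. Other shapes and a looser distance.** At 1.5 m, a 32-inch screen allows 16.3° vertically in 16:10 and 19.2° in 5:4. At 1.3 m, a 27-inch 16:9 screen allows 25.9° horizontally and 14.7° vertically; a 32-inch one allows 17.4° vertically. The most generous case tried (32-inch 5:4 at 1.3 m) reaches 22.1°. Vertical 24° fits in none of them.

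**Step 5. Effect on the outcomes.** Suppose the eye covers 95% of the on-screen jump, the true distance is shorter than 1.5 m, and both eye and target are converted at 1.5 m. The 95% and the true distances are illustrations, not figures from the protocol.

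| True distance | Position error, 24° jump (true 1.17°) | Position error, 14° jump (true 0.69°) |
|---|---|---|
| 0.50 m | 0.40° | 0.23° |
| 0.65 m | 0.52° | 0.30° |
| 1.00 m | 0.80° | 0.47° |
| 1.30 m | 1.02° | 0.60° |

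The scale factor is close to true distance ÷ 1.5, and velocity in °/s scales in about the same way. Gain stays at 0.950 to 0.951 throughout, because the conversion nearly cancels in a ratio.

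Gain is distorted in a different case. On a 24-inch 16:9 screen at 1.5 m, a 24° vertical jump would be cut to 11.38°. A perfect saccade scored against the nominal amplitude would then give 11.38/24 = 0.47.

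**The case against.** The strongest reply is that the conflict rests on a screen size the protocol does not give. A monitor of about 29 inches shows every horizontal reflexive jump, and one of about 51 inches shows the whole reflexive test. The distance is only approximate, and at 1.3 m a 27-inch screen covers the full horizontal range. This stands for the horizontal jumps. It does not rescue the vertical set: 51 inches is not a desktop monitor in the ordinary sense, and a moderately shorter distance or a squarer screen recovers only the smaller vertical amplitudes.

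The self-paced wording can be read as 15° apart. That needs 39.5 cm and fits even a 19-inch 16:9 screen. The two outcomes of that test are not measured against target amplitude in any case. This also stands.

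A reader might infer that gain and position error will be wrong. The documents do not support that. A target that does not fit is missing or shortened, which is not the same as mis-measured. A scaling error needs a true distance different from the one in the software, and the protocol does not say which distance the software uses.

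A reader might also infer a biased collar comparison. All functional testing takes place in one laboratory under one procedure. A scale factor common to both groups and both sessions changes the reported degrees but barely affects the group-by-session tests. Nothing in the documents suggests that distance would differ by group or visit; the point is only that such a difference would go unrecorded.

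**Conclusion.** The point holds for the vertical jumps. On 16:9 screens of 19 to 32 inches at 1.5 m, at least five of the six vertical amplitudes cannot be shown, and all six fail up to 27 inches. This depends on the assumed screen range, but 24° vertical failed for every shape tried, even at 1.3 m. The horizontal 24° jump is in doubt only below about 29 inches, and the self-paced targets only below about 36 inches and only if they are 30° apart.

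As written, vertical targets would be cut off or dropped, or participants would sit closer than stated. Velocity and position error are mis-scaled if the actual distance differs from the one used for conversion. Gain is distorted only if a cut-off target is scored against its nominal amplitude. Latency, refixation counts and imaging outcomes are not mis-scaled. The correction is worth making because stated figures conflict and the remedy is cheap; no threat to the trial's main imaging comparison is shown.

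**What to change.** In Station II and in the MATLAB routine, set one geometry in which screen size, viewing distance and amplitudes all fit. There are two ways:

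- **Shorten the distance.** For 24° vertical, a 24-inch 16:9 screen must be within 0.299/(2 × tan 12°) = 0.70 m, and a 27-inch one within about 0.79 m. For targets 30° apart horizontally, about 0.99 m suffices on 24 inches. These sizes are examples. Check the chosen distance against the eye tracker's specification, which the protocol does not give.
- **Keep 1.5 m and reduce the amplitudes** to what the screen in use can show.

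State whether ±15° means 15° or 30° between targets. Record eye-to-screen distance at each visit, compute degrees from it, and score gain against the target amplitude actually displayed.

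The cost is a text correction, a software setting and a brief added measurement per visit. If 1.5 m is kept, smaller saccades are tested.

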### **Injury Surveillance**

*Device and Compliance Acceptance:* The study coordinator will be responsible for providing the appropriate intervention (device or no-device) to each team based on their assignment prior to the season onset. At first fitting of the collar a registered vascular technologist will utilize ultrasound to ensure that the collar fits correctly and is activated as prescribed. Following the initial fitting, each athlete will receive adequate instruction on how to properly use the device on a daily basis. Throughout the season, the coordinator will make routine visits to each team to monitor the proper usage and fitting of the device, tracking the use of the device by each athlete individually. At the end of practice/game the device will be collected by the athletic trainer and/or stored in the athlete's locked locker. The device is NOT to go home with the athlete.

*New Concussion Surveillance and Follow-up:* Each participant will be provided with an X Patch accelerometer (X2 Biosystems; Seattle, Washington) The X patch adheres to the head, just behind the ear using an adhesive patch, as seen in the image below. .

X2 is a small and durable device that is attached to the back of the neck behind the ear to track impacts, and it stores data for uploading to a PC. This X2 accelerometer accurately measures the severity of impacts by converting data such as high impact collision into usable data outputs. X2 data will be used in final analysis to normalize the exposures to potential concussive events. All impacts of greater than 10 g-force will be recorded and utilized in the post-season analyses. No one besides those approved by this IRB protocol will have access to any data. If available, video of games and practices will be used to validate and confirm head impacts recorded by accelerometers.

concussion testing completed as part of the study, will be used in making any clinical decisions for return to play.

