**(1) ABSTRACT:**

Significant morbidity, mortality, and related costs are caused by traumatic brain injury (TBI). A simple, effective, and lightweight device worn by athletes or war fighters in the field, designed to mitigate TBI resulting from blast trauma or concussive events, would save lives, and the huge costs incurred for life-treatment of surviving victims. An externally-worn medical device (the Device) that applies mild jugular vein compression according to the principle of the Queckenstedt Maneuver, is being developed by Q30 Sports Science, LLC (Q30). Preliminary research suggests that the Device has the potential to reduce the likelihood of TBI. The currently developed collar (Smith 2009, Smith and Fisher 2011, Smith and Fisher 2011, Smith 2012) has been approved for studies in humans (IRB 2013-2240) and the results indicate safety for use during high demand and maximal exertion activities. Regarding safety, the externally worn collar is meticulously designed to mimic the body's own omohyoid muscle actions upon the jugular veins that will provide similar pressure and volume increases not to surpass that of a yawn or the mere act of just lying down.

This study will investigate the effectiveness of this device in high school athletes playing a non-helmeted sport such as soccer. Athletes participating in this study will be randomly assigned to one of two groups: 1) Device wearing during the season or 2) Non-device wearing during the season. This study will focus on the use and effectiveness of the device solely in females, as male football and hockey players have previously been investigated. All participants will be outfitted with an adhesive patch-like accelerometer (which will be placed behind the ear (*Xpatch-X2 Biosystems* [http://www.x2biosystems.com/x2\\_x\\_patch/](http://www.x2biosystems.com/x2_x_patch/)) which will measure the magnitude of every impact to the head sustained by the athlete. Effectiveness of the device will be determined via differences in longitudinal brain imaging and functional testing following competitive soccer participation. A subset of athletes who report a diagnosed concussion will also receive additional brain neuroanatomical and neurophysiological testing within a week following the diagnosed concussive event. At each of these time points participants will also undergo various neurocognitive assessments outlined below.

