**(6) SELECTION & RECRUITMENT OF PARTICIPANTS:**

We will recruit up to 150 study participants. The participants (age 14-19 years old) will be recruited from a local school district and local sports clubs and teams. Participants will be recruited using a top-down approach. We have gained the consent and the cooperation of the school district administrations. Presentations and letters from the research team will be given to each participating school to detail the participation requirements and study risks.. Questions regarding participation will be answered during the presentations or through e-mail or phone. Participants will be contacted via telephone to further explain the study, answer any additional questions and to enroll them in the study. The participants and parents/guardians who voluntarily agree to participate will be scheduled to complete the pre-participation testing. The participant and parent/guardian will read and sign the “Consent to Participate in a Research Study” form, approved by the Institutional Review Board of Cincinnati Children’s Hospital. If the participant and parent/guardian does not read or sign the form, they will not participate in the study. Once the potential study participants/school teams are identified, they will be allocated to one of two groups: 1) Device wearing during the season or 2) Non-device wearing during the season. This research does not mandate that the participant maintains participation in their sport. The desire to participate in the sporting event is an independent, personal decision separate from the decision to enter into this study. If any athlete chooses to stop participation in the sporting activity then they will also be withdrawn from the study, due to no longer meeting inclusion criteria.

Inclusionary criteria include:

- Female

- Normal healthy volunteer
- Able to provide written consent
- Must be 14 years or older and a participant on a high school soccer team

Exclusionary criteria include:

- Unable to provide written consent
- History of neurological deficits, previous cerebral infarction, or severe head trauma as indicated through pre-season screening:
- Medical contraindications to restriction of venous outflow via the internal jugular veins (known increased intracerebral pressure, metabolic acidosis or alkalosis)
- Glaucoma (Narrow Angle or Normal Tension)
- Hydrocephalus
- Recent penetrating brain trauma (within 6 months)
- Known carotid hypersensitivity

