### ***Data Analysis.***

Data processing and analysis will be performed using a series of existing software including FSL (FMRIB's Diffusion Toolbox in FSL Software, Oxford, UK), AFNI (Cox, 1996), SPM (Statistical Parametric Mapping analysis package, Wellcome Department of Cognitive Neurology, London, UK), DTIStudio (John Hopkins University, Baltimore, MD; Jiang et al., 2006), as well as additional customized software written in Matlab or IDL.

DTI data will first be subjected to preprocessing to correct for Eddy current and head motion artifact, followed by calculation of the three diffusion eigenvectors and eigenvalues. DTI measures, including fractional anisotropy (FA), mean diffusivity (MD), axial diffusivity (AD), and radial diffusivity (RD) will be calculated. The regions of interest will be manually determined in major white matter areas such as corpus callosum, internal capsule, and external capsule. After being normalized to a common template, voxel based group analysis can be performed to explore brain regions that present significant group difference or longitudinal changes. Fiber tracking can be performed to generate white matter tracts in different areas in the brain, e.g., cortico-spinal tract, different segments in corpus callosum, optic radiation, cingulum superior longitudinal fasciculus, and others.

Functional fMRI (resting state fMRI) will also be subjected to routine image pre-processing pipeline. Functional connectivity analysis will be performed, using the CONN toolbox, <http://www.nitrc.org/projects/conn/>) between all brain regions that are involved in the proper functioning of default mode network, sensory motor network, visual network, and a series of other networks that are known to be strongly functionally connected during resting state. SWI, HARDI and ASL BOLD will undergo standard image post-processing.

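### The unit of assignment is inconsistent (athletes or teams); if teams are assigned, no stated collar comparison names team, and athlete-level tests exceed .05 whenever positive within-team correlation remains in the change or adjusted residual

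*Combined protocol and SAP*

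**What the plan says.** Three places describe who is assigned, and they do not agree.

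- Section 1 (Abstract): "Athletes participating in this study will be randomly assigned to one of two groups". The unit is the athlete, and this is the only one of the three that describes the assignment as random.
- Section 6 (Selection and Recruitment): "Once the potential study participants/school teams are identified, they will be allocated to one of two groups". The unit is left open, and no method of allocation is given.
- Section 8 (Injury Surveillance, Device and Compliance Acceptance): the coordinator is responsible for "providing the appropriate intervention (device or no-device) to each team based on their assignment prior to the season onset". The same paragraph also has the coordinator "tracking the use of the device by each athlete individually".

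The number of teams is not stated. Section 6 says only that participants are "recruited from a local school district and local sports clubs and teams".

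Section 9 sets out the collar comparisons:

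- Data Analysis: "voxel based group analysis can be performed to explore brain regions that present significant group difference or longitudinal changes".
- Statistical analyses: an ANCOVA on time and condition, and a secondary Poisson model with a playing-time offset, fitted in a procedure said to allow fixed and random effects.
- Simple Reaction Time and Oculomotor Measures: 3 x 2 group-by-time ANOVAs.
- Statistical considerations: "Candidate predictors include amount of playing time, amount of practice time, previous mTBI, weight, age and height", and "statistical tests are considered two-sided and a .05 significance level is used".

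Team, school and club appear in none of these as a covariate, stratum, random effect or cluster.

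**The concern.** The unit of assignment determines which standard error is valid. If whole teams receive one condition, the collar effect is estimated from differences between teams, and the relevant replication is the number of teams. An analysis that treats about 150 athletes as independent then has standard errors that are too small whenever teammates' changes resemble each other. Such resemblance is plausible, because teammates share a schedule, coaching and a head-impact environment.

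A difference between teams could then be reported as a device effect. This would reach the pre-to-post imaging comparison, which is the study's first stated purpose. In the 3 x 2 designs, the term mixed-model refers to group by time, so it does not deal with team.

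**Working it through.** **1. Inputs.** From the documents: up to 150 participants (section 6), two groups (section 6), two-sided .05 (section 9). Not in the documents, so assumed: 1:1 allocation, equal teams, the number of teams, and the within-team correlation (ICC) of the pre-to-post change or baseline-adjusted residual. The calculation covers one continuous outcome tested once. The results are not voxelwise or Poisson error rates.

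**2. The plan's own figure.** With independent athletes, 2 × (1 − Φ(1.96)) = .050, which is the stated level. The figure of 150 cannot be reproduced, because no effect size, SD or power is given.

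**3. Athlete-level test under team assignment.** With m athletes per team, the design effect is DE = 1 + (m − 1) × ICC, and the actual type I error is about 2 × (1 − Φ(1.96/√DE)).

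Worked case, 10 teams of 15 at ICC .05: DE = 1 + 14 × .05 = 1.70; 1.96/√1.70 = 1.503; error = .133.

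| Teams × athletes | ICC .01 | ICC .05 | ICC .10 |
|---|---|---|---|
| 14 × 11 | .062 | .110 | .166 |
| 10 × 15 | .066 | .133 | .206 |
| 6 × 25 | .078 | .186 | .288 |
| 4 × 38 | .094 | .246 | .366 |

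At ICC .005 the 4-team case gives DE = 1.185 and an error of .072.

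**4. Simulation check.** With 20,000 null trials per cell, a baseline-adjusted athlete-level ANCOVA (assumed pre-post correlation .7) gave .068 / .131 / .207 for 10 teams and .077 / .184 / .291 for 6 teams at ICC .01 / .05 / .10. With 4 teams, the simulated athlete-level t-test gave about .09 / .25 / .38. At ICC 0 the ANCOVA gave .051.

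**5. When the problem disappears.** With simple randomisation of athletes and team ignored, simulated error was 4.8–5.4% across 2 to 10 teams and ICC 0 to .10. With athletes balanced within teams and team ignored, it was about 4.1% at ICC .10, which is slightly conservative. Under team assignment, a t-test on team means held 4.6–5.2% with 4 to 10 teams.

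**6. Cost in power if teams are assigned.** Detectable difference at 80% power, noncentral t, SE = √(4 × DE/150), df = teams − 2. Under independence (df 148) it is 0.46 SD.

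| Teams | ICC .01 | ICC .05 |
|---|---|---|
| 10 | 0.56 SD | 0.68 SD |
| 8 | 0.60 SD | 0.76 SD |
| 6 | 0.68 SD | 0.91 SD |
| 4 | 1.08 SD | 1.56 SD |

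**The case against.** The strongest reply is that team assignment is not established. The abstract alone describes the assignment as random, and its unit is the athlete. The section 8 sentence describes a coordinator's delivery task, and the assignment it mentions can be read as the athletes' own. The coordinator also visits each team to check use and fit, which suits a design with device wearers on every team. This stands as a possible reading. It does not remove the conflict, because section 6 still names participants and teams as alternatives. Per-athlete tracking is compliance monitoring and fits either design.

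A second reply is that the residual ICC may be small. Playing time and practice time are candidate predictors, accelerometer data are meant to normalise exposure, and the design and facilities sections place all MRI on one scanner at one centre. Section 8 also lets athletes with metal be left out of imaging, so fewer per team may be scanned. With 10 rather than 15 per team at ICC .05, DE = 1.45 and the error is .104 rather than .133. All of this could reduce the inflation. It does not make the ICC zero, and the plan does not argue that it is. The predictor list is open, so team could be added, but the plan does not say that it will be. The random-effects remark might be meant to cover team, but it names no grouping unit and reaches only the Poisson model.

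A reader might infer that this is a cluster-randomised trial with a known error rate several times .05, or that it has one team per arm so that collar and team cannot be separated. The documents support neither. They do not fix the unit or give an ICC, and section 6 speaks of schools, clubs and teams in the plural.

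**Conclusion.** The contradiction over the unit of assignment is in the current text and needs correcting. The statistical harm is conditional on two facts the documents do not give: that teams are assigned, and that a positive within-team correlation remains in the pre-to-post change or adjusted residual. Correlation in the raw outcome alone is not enough.

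If both hold, the stated athlete-level comparisons exceed .05. The direction does not depend on the assumed values, but the size does. Over the assumed range it runs from about 6% (14 teams, ICC .01) to about 38% (4 teams, ICC .10), and these figures are illustration only. If athletes are individually randomised, or the residual ICC is zero, the level is not exceeded. It would go too far to say that the trial's error rate is inflated. What can be said is that the plan does not fix the unit on which the validity of its collar comparisons depends.

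**What to change.** State one unit of assignment, in the same words, in sections 1, 6 and 8. This should be done before assignment, since the number of teams per arm cannot be repaired afterwards.

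**If teams are assigned:**
- Give the number of teams per arm, which must be more than one.
- Account for team in every collar comparison, including imaging, using between-team degrees of freedom. A team random intercept with a small-sample correction would do, as would a test on team-mean pre-to-post changes.
- Name team as the grouping unit in the Poisson model.
- If a permutation test over team labels is considered, note its smallest two-sided p with an equal split: 2/C(6,3) = 2/20 = .10 for 6 teams and 2/C(4,2) = 2/6 = .33 for 4. Neither can reach .05, whereas a team-means t-test remains usable.

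The cost is wider intervals and lower power, severe with about 4 teams (1.08 to 1.56 SD detectable against 0.46 SD under independence). Recovering the power would need more teams, which is more than a wording change.

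**If athletes are assigned:**
- Reword sections 6 and 8 so that the collar is provided according to each athlete's assignment.
- If randomisation is stratified by team, include team in the models.

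Power is kept. The cost is that collars are issued athlete by athlete and teammates see both conditions. Section 8 already tracks use individually.
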